**Title: Connectivity Affecting the Antidepressant Response (CAARE)
Study Protocol**

Clinicaltrials.gov Identifier: NCT02332291

NIH Grant: R01 MH102246

NIH Grant Title: Neural Connectivity Affecting the Antidepressant Response: Testing a Lesion Model

Document Date: 4/10/2020

Connectivity Affecting the Antidepressant Response (The CAARE study)

NIH Grant: R01 MH102246

NIH Grant Title: Neural Connectivity Affecting the Antidepressant Response: Testing a Lesion Model

Clinicaltrials.gov Identifier: NCT02332291

PI: [name], MHSc
Department of Psychiatry
Vanderbilt University Medical Center
[name]
[name]

1.0 BACKGROUND:

Individuals with late-life depression (LLD) experience high levels of disability, mortality, and poor responses to antidepressants. Age-related white matter disease is characteristic of LLD and contributes to these poor outcomes (1). Although the underlying mechanisms are not well established, white matter disease may contribute to LLD by adversely affecting cognitive, affective, and default mode networks. This project's primary goals are to characterize whether focal vascular damage to specific white matter tracts: a) affects neural circuit connectivity & function, b) influences clinical presentation, and c) predicts poor response to antidepressants.

The MRI hallmark of 'vascular depression' is significant ischemic white matter lesion (WML) severity (2), a finding associated with poor antidepressant outcomes. Despite observations of diffuse white matter disease in LLD, we propose in our "disconnection hypothesis" (3) that focal damage to fiber tracts negatively affects the function of connected regions, resultantly contributing to cognitive deficits and clinical symptoms such as depression severity and negativity bias. Focal WMLs may also reduce the likelihood of an antidepressant response *when the specific antidepressant used acts on neurotransmitter systems projecting through the damaged fiber tract*. This implies that the effect of tract damage on clinical response may *differ between drugs with different mechanism of action*. We propose that the **cingulum bundle (CB)** and **uncinate fasciculus**

(UF) are key tracts in LLD as they are components of cognitive, affective and default mode networks and contain monoamine neurotransmitter projections. Supporting our model, past work implicates CB and UF deficits in LLD (4-7) and our recently published data associates tract damage in the CB with poor antidepressant response (8).

This study has broad *significance* for elucidating how vascular factors influence the occurrence and course of LLD. It provides a scientific opportunity to use a neuroimaging finding of known pathology (WMLs) to examine how circuit deficits adversely affect antidepressant response. Importantly, clinical translation of this work may guide individualized treatment. Knowledge of circuit-response relationships may inform antidepressant selection or the identification of individuals likely to be treatment-refractory. We propose that we may translate this work into clinical use by linking impairment in circuits and tracts with performance on specific cognitive measures. Such measures can then be used as markers of focal tract damage.

2.0 RATIONALE and SPECIFIC AIMS:

In a cohort of 130 depressed elders we will test our **central hypotheses: a) focal CB and UF WMLs disrupt connectivity and function of connected regions and contribute to cognitive deficits and affective symptoms; and b) antidepressants acting on neurotransmitter systems projecting through these tracts will be less effective**. We will examine how novel measures of tract-specific WML volumes are associated with neural connectivity (using resting state fMRI), reactivity to cognitive & affective stimuli (using a fMRI task), & clinical presentation. After MRI, participants will be stratified by WML volume and randomized to blinded escitalopram (5HT) or placebo. Participants who do not remit in this initial phase will then receive open-label bupropion (DA/NE). These drugs affect different neurotransmitter systems with distinct projection pathways. This design will allow us to examine both drug and placebo responses while also testing whether discrete neural circuit deficits differentially affect drug response.

Specific Aim 1: To characterize the effect of cingulum bundle (CB) and uncinata fasciculus (UF) WMLs on

Protocol Version: 2.0

Protocol Date: 04/10/2020

tract connectivity, function of connected regions, and the cognitive and affective presentation of LLD (Fig 1&2).

Hypothesis 1: Greater CB WML volume is associated with a) reduced resting-state connectivity of frontal, temporal, and cingulate regions and b) deficits in attention, memory and processing speed.

Hypothesis 2: Greater UF WML volume is associated with a) reduced resting state functional connectivity between frontocingulate and medial temporal regions, and b) greater depression severity and negativity bias.

Exploratory Hypothesis: Greater CB WML volume is associated with failure of anterior and posterior DMN nodes to deactivate during attentional components of the fMRI task. Greater UF WML volume is associated with greater medial temporal reactivity during affective components of the fMRI task.

Specific Aim 2: To determine whether deficits in tract structural / functional connectivity predict nonremission to antidepressant treatments and if these relationships vary based on antidepressant mechanism of action.

Hypothesis 3: Nonremission to escitalopram will be predicted by: a) greater WML volume in the CB and UF, and b) reduced resting functional connectivity between structures connected by the CB and UF. Greater WML severity and reduced functional connectivity in these tracts will not significantly predict response to placebo.

Hypothesis 4: Nonremission to bupropion will be predicted by a) greater WML volume in the UF but not CB, and b) reduced resting functional connectivity deficits between structures connected by the UF but not CB.

Exploratory Aims: **Expl. Aim 1)** To determine if specific cognitive measures may serve as markers of focal tract WML damage. **Expl. Aim 2)** To use whole-brain multimodal imaging approaches to examine how connectivity differences in other brain regions may also predict nonremission to antidepressants.

For exploratory analyses, we will also recruit 30 elders with no psychiatric history. Data from this population will help us understand whether our neural and cognitive findings in depression represent differences from what is seen in healthy aging, or whether our observations in depressed elders are within the range of normal aging. This will be important for data interpretation and planning for future projects.

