maladaptive cognitive processes (61,65). In MDD we observe a dissociation between anterior and posterior DMN nodes (66) while within-node functional connectivity is increased (38,46,63,64). As reduced functional connectivity is related to altered CB structure (67,68), we propose that WMLs in the CB adjacent to the cingulate gyrus may disrupt communication between DMN nodes. This would impair anterior-posterior connectivity, resulting in difficulty coordinating deactivation of the DMN during tasks (61). This contributes to deficits in **attention** (69,70) and **processing speed** (59,71-73), deficits associated with poor antidepressant response (21,57). *Additionally*, damage to the CB in the region of the hippocampus may have further effects. WMLs in this region may disrupt hippocampus-posterior cingulate connectivity (31,47,74) resulting in poorer episodic memory performance (75-77). This results in **episodic memory deficits** that are also associated with poor LLD antidepressant responses (21) (Figure 2.c).

3.4. Antidepressants with different mechanisms of action: Antidepressant treatment changes brain metabolism (78-82). However, antidepressants with different mechanisms of action have different effects on neural circuit connectivity (83,84) or neural activity during tasks (85,86).

The relationship between neural circuit deficits and the antidepressant response may *depend on the drug's specific mechanism of action*. We hypothesize that tract damage predicts nonresponse to antidepressants that affect neurotransmitter systems projecting through that tract. Serotonergic neurons project widely through the CB (87), but also to the orbitofrontal cortex and medial temporal lobe (88-90), suggesting UF involvement. Noradrenergic projections largely overlap with serotonergic innervation (91), including CB projections (92). In contrast, dopaminergic neurons have discrete pathways (93-96). Dopaminergic mesocortical and mesolimbic fibers may pass through the UF (97), but compared to serotonin or norepinephrine, have less CB projections (98). *Thus drugs affecting serotonin and norepinephrine may require intact connectivity in both the CB and UF, while dopaminergic agents may depend less on the CB.*

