This approach will slightly differ for each study phase. For Phase 1, models will include drug arm (placebo or escitalopram). To examine for differences in how tract impairment affects remission in each arm, we will test for interactions between drug assignment and tract integrity (WML & FC). We will explore significant interactions in individual models. For subjects entering Phase 2, we will test for differences in tract integrity (WML & FC) between those originally assigned to escitalopram and placebo. If differences are observed, in models we will control for original Phase 1 cohort assignment. In exploratory models, we will use similar approaches to test for the additional effect of cognitive domain function (Table 5) on remission. We will also use this approach for Exploratory Aim 2 when we examine the effect of connectivity deficits in other tracts.

Importantly, the relationship between connectivity and antidepressant response may not be linear. It is possible that a ‘threshold’ must be crossed in order for tract connectivity deficits to influence response (3). To properly take into account nonlinear effect of a continuous predictor variable (e.g., WML, FC) on response variable (e.g., remission or nonremission) in the models, we will employ restricted cubic splines of the predictor. Statistical significance of the nonlinear terms via F-test implies that the relationship between the two measures of interest can be nonlinear.

15.1. Sample Size and Statistical Power:

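### Aim 2 asks whether tract effects depend on antidepressant mechanism, but no planned analysis contrasts escitalopram with bupropion

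*Combined protocol and SAP*

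**What the plan says.** Section 2.0 presents the design as "testing whether discrete neural circuit deficits differentially affect drug response", and Specific Aim 2 asks "if these relationships vary based on antidepressant mechanism of action". Section 3.4 gives the premise: "drugs affecting serotonin and norepinephrine may require intact connectivity in both the CB and UF, while dopaminergic agents may depend less on the CB".

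The hypotheses are worded drug by drug:
- Hypothesis 3, on escitalopram: "Nonremission to escitalopram will be predicted by: a) greater WML volume in the CB and UF". The same measures "will not significantly predict response to placebo", it adds.
- Hypothesis 4, on bupropion: "Nonremission to bupropion will be predicted by a) greater WML volume in the UF but not CB".

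Section 15.0 introduces the phase-specific analyses with "This approach will slightly differ for each study phase".
- Phase 1: "For Phase 1, models will include drug arm (placebo or escitalopram"), with interactions between drug assignment and tract integrity. Significant interactions are then explored in individual models.
- Phase 2: baseline tract measures are compared between participants who came from the two Phase 1 arms. If they differ, original arm is added as a covariate.

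Section 15.1 powers Aim 2 for Phase 1 only. It gives no figure for any comparison of escitalopram with bupropion.

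**The concern.** The Phase 1 interaction separates active drug from placebo. It does not separate a serotonergic mechanism from a dopaminergic/noradrenergic one. The Phase 2 step is a rule for choosing a covariate and says nothing about whether the tract slope differs between drugs. No model contains both active drugs.

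An analyst who follows the plan exactly will have a CB coefficient under escitalopram from one model and a CB coefficient under bupropion from another, with no estimate of their difference. The hypotheses are phrased as predicted by and not predicted by, so the natural reading is to compare significance across phases. The two samples differ in size and in how they were selected, and a difference in significance is weak evidence of a difference in effect. At stake is the second clause of Aim 2 and the suggestion in Section 1.0 that such findings may inform antidepressant selection.

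**Working it through.** **The plan's own figure.** Section 15.1 says that 130 participants allow detection of a log hazard ratio of 0.45 for one measure, with base nonremission 0.36 and covariate R² 0.10. It states no power for this. The logistic formula for a continuous predictor gives Φ(0.45 × √(130 × 0.36 × 0.64 × 0.90) − 1.96) = Φ(0.38) = 65%. The Cox formula with 0.36 as the event rate gives Φ(0.45 × √(130 × 0.36 × 0.90) − 1.96) = 83%. Without a stated power, reproduction cannot be settled. Neither figure concerns a between-drug contrast.

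**Inputs from the documents.** 130 evaluable (Section 4.0); 2:1 allocation (Section 9.1), so about 87 on escitalopram and 43 on placebo; bupropion for Phase 1 nonremitters (Sections 2.0 and 7.0); base nonremission 0.36 and R² 0.10 (Section 15.1).

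**Assumptions.** The documents give no Phase 2 sample size or remission rate. I take Phase 1 nonremission from 36% to 60%, which gives 130 × 0.36 ≈ 47 to 130 × 0.60 = 78 entrants with no dropout between phases. The CB odds ratio is the same under both active drugs, and tests are two-sided at 0.05.

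**Worked case by formula.** Log OR 0.45 per SD for both drugs, Phase 1 nonremission 36%, Phase 2 nonremission 50%:
- Escitalopram: SE = 1/√(87 × 0.36 × 0.64 × 0.90) = 0.235; power = Φ(0.45/0.235 − 1.96) = 48%.
- Bupropion: SE = 1/√(47 × 0.50 × 0.50 × 0.90) = 0.308; power = Φ(0.45/0.308 − 1.96) = 31%.
- Escitalopram significant and bupropion not, treating the phases as independent: 0.48 × (1 − 0.31) = 33%.

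With nonremission in each phase varied from 36% to 64% (47 to 83 entrants), the same formula gives 24% to 34% at log OR 0.45 and 19% to 39% at 0.60.

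**Simulation.** 87/43 randomised; equal CB odds ratio of about 1.6 to 2.0 under both drugs and no effect under placebo; Phase 1 nonremission 36% or 60%; Phase 2 nonremission 50% or 65%.

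| Event, with no true difference between drugs | Share of trials |
|---|---|
| Escitalopram significant, bupropion not | about 17% to 43% |
| The same, and Phase 1 interaction also significant | about 8% to 18% |
| Direct test of the slope difference rejects | about 5% |

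**Selection.** Assume an unmeasured prognostic factor with log OR 1 per SD and a conditional CB odds ratio of 2.0. The marginal odds ratio without selection is about 1.78. Among escitalopram failures the bupropion CB odds ratio is about 1.65; among placebo failures it is about 1.81.

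**What a direct contrast can deliver.** In the worked case the SE of the slope difference is √(0.235² + 0.308²) = 0.387. If the true log OR is 0.45 on escitalopram and 0 on bupropion, power is Φ(0.45/0.387 − 1.96) = 21%. The difference detectable with 80% power is 2.80 × 0.387 = 1.09. Over the 36% to 64% grid these are 20% to 28% and 0.92 to 1.11.

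**The case against.** **The Phase 1 interaction is a safeguard.** If an escitalopram-specific slope is interpreted only after a significant interaction with placebo, the misleading pattern falls to about 8% to 18%. That stands and is why both ranges are given. The gated range is still above the roughly 5% of a direct test.

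**The frequencies need a real CB effect.** At a common odds ratio of 1.2 the pattern appears in 10% to 11% of trials ungated and 2% to 3% gated; at 1.0, in about 2% or less. This also stands.

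**The plan nowhere says that discordant significance will be declared a drug difference.** A reader might infer that it does. The documents do not support that: Hypotheses 3 and 4 are within-drug predictions, and the contrast of the uncinate fasciculus (UF) with the CB in Hypothesis 4 lies within one bupropion sample, so unequal phase sizes do not create it. The simulation covers the CB alone and does not require the UF to predict. What remains is that Aim 2 asks a between-drug question and the plan supplies nothing else to answer it.

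**Selection might seem to explain the predicted absence of a CB effect on bupropion.** Setting 1.65 against the conditional 2.0 suggests a large shrinkage, but most of that drop is non-collapsibility of the odds ratio, which is present without any selection. Selection accounts for about 1.78 to 1.65, only among escitalopram failures, and under a factor that the documents do not describe.

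**A contrast would be weak and confounded.** True. Drug is tied to phase, open-label use and Phase 1 nonremission, and power is low. That argues for showing the interval and limiting the claim; it does not argue for leaving the contrast out.

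**Conclusion.** The gap is real: Section 15.0 contains no analysis that contrasts escitalopram with bupropion, although Aim 2 asks for one. Comparing significance across the separate phase models would suggest the predicted CB difference in about 17% to 43% of trials with no true difference, or about 8% to 18% with the Phase 1 interaction as a gate, against about 5% for a direct contrast. These ranges rest on an assumed common odds ratio of about 1.6 to 2.0 per SD and on assumed Phase 2 numbers and nonremission rates. Selection adds a modest attenuation at most.

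Two stronger readings should be resisted. The gap does not undermine Aim 2 as a whole, because its first clause, whether tract deficits predict nonremission, is addressed by the planned models. Nor would a contrast make the mechanism question well answered, since the sequential design limits it whatever the analysis.

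**What to change.** Add to Section 15.0 a stacked model with one row per participant per phase, participant-clustered standard errors and the Aim 2 covariates (baseline MADRS, age, sex, vascular risk). Fit it separately for each tract measure, with treatment (placebo, escitalopram, bupropion) by tract terms. Prespecify the escitalopram-versus-bupropion slope contrast and report it with a 95% CI.

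State that any conclusion that tract effects differ by mechanism rests on that contrast and not on discordant significance across phases. Label it a low-powered, non-randomised comparison confounded with phase, open-label use and Phase 1 nonremission.

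A repeat limited to bupropion entrants who came from placebo avoids selection on escitalopram outcome, but it would have only about 15 to 26 people (43 × 0.36 to 43 × 0.60). It should be descriptive only.

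The cost is some SAP text and one further model form on data already collected. The downside is a wide interval for the between-drug claim.

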4.0 ENTRY CRITERIA

We plan to enroll a cohort of 200 individuals to meet goals of having 130 evaluable subjects. Participants will meet DSM-IV-TR criteria for MDD, single episode, recurrent, or chronic. We will not be enrolling vulnerable populations, specifically pregnant women, children, prisoners, or institutionalized individuals. We also will not enroll subjects incapable of providing their own consent. Should a potential subject present where there is a concern (either by a study clinician or staff member) about their ability to understand study procedures and provide meaningful consent, their cognitive ability and understanding will be evaluated by a study doctor. If there is any concern that the individual may be impaired, they will not be enrolled in the study. The rationale will be provided to the individual as well as his or her family members. Referrals for further evaluation, including urgent or emergent evaluation, will be made as needed and clinically warranted.

Men and women of all races / ethnicities are eligible.

Depressed Cohort:

Inclusion Criteria:

- 1) Age 60 years or older.
- 2) Current diagnosis of major depressive disorder (DSM-IV-TR), single episode, recurrent or chronic, without psychotic features, as detected by MINI and clinical exam.
- 3) Minimum MADRS score ≥ 15 .
- 4) Mini-Mental State Exam ≥ 24 .
- 5) Fluent in English.

Exclusion Criteria:

Diagnostic Issues:

- 1) Current or past diagnoses of other Axis I psychiatric disorders, except for generalized anxiety disorder (GAD) symptoms occurring during a depressive episode
- 2) History of alcohol or drug dependence or abuse in the last three years
- 3) History of developmental disorder or IQ score < 70
- 4) Presence of acute suicidal ideation, defined as a "yes" response to items 3, 4, or 5 on the C-SSRS
- 5) Acute grief (< 1 month)

Protocol Version: 2.0

Protocol Date: 04/10/2020

- 6) Current or past psychosis

Medical Issues:

- 7) Primary neurological disorder, including but not limited to dementia, stroke, brain tumors, epilepsy, Parkinson's disease, or demyelinating diseases
- 8) MRI contraindications
- 9) Any physical or intellectual disability adversely affecting ability to complete assessments
- 10) Current pregnancy or capable of becoming pregnant (defined as ability to have children [i.e., has not had a hysterectomy or bilateral oophorectomy] and is not clearly postmenopausal [> 1 year of amenorrhea])

Antidepressant Treatment Issues:

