9.0. RANDOMIZATION & STUDY DRUG ADMINISTRATION

9.1. Randomization: After initial assessments, participants are randomized to double-blinded Phase 1 drug assignment (escitalopram or placebo). As our primary interest for Phase 1 is related to escitalopram response, we will allocate participants in a 2:1 drug-to-placebo ratio. Randomization will be conducted by the Vanderbilt Investigational Drug Service. Nondepressed individuals will not be randomized to study drug.

Randomization will be stratified by MRI measures of total cerebral WML volume. Our measurement of total WML volume is automated and available within 24 hours of the scan and subjects will be stratified as "high" or "low" total cerebral WML volume. Based on pilot data, we will use a cutoff of 3.86mL; this is the median 3T WML volume from a cohort of 145 depressed elders analyzed using our WML segmentation method. When we reach 50% enrollment, we will re-assess this cutoff based on study data and adjust if necessary.

If there are delays in scan processing, stratification will be determined using the Coffey-modified Fazekas visual rating scale (2), dichotomizing participants as "high" (2 or 3, confluence of foci) or "low" (0 or 1, absent or punctate foci).

MRI measures will only be used for stratification. They will not guide or determine treatment decisions.

9.2. Phase 1: Blinded Escitalopram or Placebo: We selected escitalopram due to its tolerability, ease of dosing, and lack of effects on dopamine and norepinephrine (115). The Vanderbilt IDS will prepare over-encapsulated escitalopram and matching placebo and maintain the blinded assignment in case of emergencies. Participants will receive one tablet (10mg or placebo) for at least 2 weeks. If tolerated, it can be increased to a target dose of two tablets (20mg) daily at the two-week study contact, but dosing changes will not be made at week 6 or later. For problems with tolerability, the dose can be reduced to the previous level, but not below one tablet daily.

9.3. Transition: After 8 weeks subjects will be assessed for remission (MADRS \leq 7). Those achieving remission will end their study participation. Those who are not remitted will have their Phase 1 drug tapered over a week to decrease the chance of discontinuation syndrome then progress to Phase 2.

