- a. **Escitalopram common side effects:** Although generally well tolerated, escitalopram does carry risk of side effects. These include: dermatological (rash), gastrointestinal (dry mouth, nausea, diarrhea, constipation), neurological (dizziness, vivid dreams), systemic (fatigue, somnolence or insomnia, appetite change, weight loss/gain, sweating), and sexual dysfunction.
 - b. **Bupropion common side effects:** Likewise, bupropion is generally well tolerated. Common side effects include: dermatological (rash), gastrointestinal (nausea, diarrhea, constipation, dry mouth), neurological (dizziness, headache, tinnitus, tremor, vivid dreams), psychiatric (anxiety, agitation), or systemic (insomnia, appetite and/or weight loss, sweating). There are also rare risks of seizures or Stevens-Johnson syndrome, which we address through our entry criteria.
 - c. **Suicide risk:** Antidepressant-induced suicidality is an important concern and one that has resulted in a black-box warning on antidepressants by the FDA. We will both inform subjects of this potential risk and monitor for suicidality at each contact. Should any possible suicidality be detected, a study doctor will assess that individual and act accordingly (see Item 1 above).
 - d. **Discontinuation Syndrome:** Discontinuation syndrome, seen with abrupt cessation of antidepressant drugs, may cause a variety of neurological (dizziness, vertigo, insomnia, tremor, paresthesias), gastrointestinal (nausea, abdominal cramping), systemic (lethargy, flu-like symptoms) and psychiatric symptoms (irritability, anxiety, dysphoria). We will provide a medication taper for individuals who wish to stop escitalopram at the study's end.
4. **Risk of Placebo:** The primary concern with use of placebo is that individuals receiving placebo will fail to improve or worsen over the course of the placebo period. We minimize this risk by using a shorter study (8

weeks in contrast to 10 or 12 weeks) and use of withdrawal criteria, including worsening depression (“stopping rules” – see Section 12 below). We further minimize this risk by an unequal allocation of subjects in phase 1 to escitalopram or placebo in a 2:1 ratio. Such an approach is feasible as we are not testing for drug efficacy but examining neural predictors of remission, which we hypothesize would differ between escitalopram and placebo.

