Aim 1: From our published report (129) correlations of the FC of the PFC with the amygdala and the hippocampus were in the range of 0.52 to 0.55. A sample of 130 subjects, will have > 90% statistical power for associations ≥ 0.30 (two-tailed $\alpha = 0.05$). However, our primary approach to the analysis of Aim 1 will use canonical correlation with no known powering algorithms; sample size and effect estimates are used to guide the appropriateness. Using the multiple regression approach (single dependent) as a conservative estimate, a sample size of 130 achieves 83% statistical power to detect an R^2 as small as 0.06 (standardized beta = 0.20, 6% shared variance) attributed to the association of WML with a significance level (alpha) of 0.05 after adjusting for other proposed covariates. These calculations assume that the variables for which we are adjusting have an R^2 of 0.10 (10%) (130). We suspect that the control variables will have a higher inter-correlation value, thus increasing our power for testing the effect of a single variable.

Aim 2: The study includes a placebo arm to identify effects specific to an active depressant while having a comparable number of subjects receiving each active drug. Powering the study for Phase 1, Table 2 presents estimates for our proposed sample size using unadjusted effects of low vs. high WML values on the respective

outcomes of interest found in our preliminary data. The logistic regression approach allows for the testing of effects adjusted for known covariates. Using this approach, assuming a base non-remittance rate of 0.36 (36%), a sample size of 130 will enable us to detect a log hazard ratio as small as 0.45 for a specific measure. We conservatively included an assumption that covariates would account to up to 10% share of the effect on nonremission. If that value is less, our statistical power will increase for the same hazard ratio. Using high vs. low tract WML volume as an example, after controlling for other effects, our sample will enable us to detect an effect on the likelihood of non-remittance of at least 25% (high WML vs. low WML, $0.45 / 0.36 = 1.25$ or 25% increase). Continuous as well as nonlinear operationalization of effects will be examined.

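### Hypothesis 3 words the lack of a placebo association as a non-significant result, but an arm of about 43 is too small to show that lack

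*Combined protocol and SAP*

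**What the plan says.** Hypothesis 3, under Specific Aim 2 in Section 2.0, has two parts. The first predicts that tract lesion volume (WML) and reduced functional connectivity (FC) will predict nonremission on escitalopram. The second says: "Greater WML severity and reduced functional connectivity in these tracts will not significantly predict response to placebo". No margin, equivalence bound or confidence-interval rule accompanies it.

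The arm size follows from two statements. Section 4.0: "We plan to enroll a cohort of 200 individuals to meet goals of having 130 evaluable subjects". Section 9.1: "we will allocate participants in a 2:1 drug-to-placebo ratio", with the reason that Phase 1 is mainly about escitalopram response.

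Section 15.0 puts drug arm in the Phase 1 models and tests interactions between arm and tract integrity. It then says: "We will explore significant interactions in individual models". Section 12.0, item 4, puts the idea as a contrast: "examining neural predictors of remission, which we hypothesize would differ between escitalopram and placebo".

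For Aim 2 power, Section 15.1 says that "a sample size of 130 will enable us to detect a log hazard ratio as small as 0.45 for a specific measure". It takes a base nonremission rate of 0.36 and a covariate share of up to 10%. It states neither the scale of 0.45 nor the power behind it, and it gives no power for the placebo arm or for the interaction.

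**The concern.** A prediction of non-significance becomes easier to meet as the sample shrinks. If the clause is judged as it is worded, a p-value above 0.05 among about 43 people would satisfy it, even if tract damage worsened outcome on placebo by as much as the study says it can detect in all 130.

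The distinction matters for interpretation. Section 15.1 says the placebo arm is there to separate out effects specific to active drug, and Section 1.0 hopes the results will guide choice of antidepressant. Tract damage that is a general marker of poor prognosis, somewhat stronger under escitalopram, is a different finding from tract damage that is irrelevant without the drug. The interaction can support a difference between arms. Only a sufficiently precise placebo slope can support irrelevance.

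**Working it through.** **Inputs.** Evaluable N = 130 (Section 4.0). Allocation 2:1 (Section 9.1), so placebo n = 130/3 ≈ 43 and escitalopram ≈ 87. Nonremission p = 0.36, covariate R² = 0.10 and effect 0.45 (Section 15.1). Assumptions: two-sided α = 0.05 (two-tailed is stated only for Aim 1), 0.45 read as log-odds per SD, and 0.36 applied to placebo, since no separate placebo rate is given.

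**1. The plan's own figure.** It has no stated power, so it cannot be strictly reproduced. For a continuous predictor in logistic regression, power = Φ(b·√[n·p(1−p)(1−R²)] − 1.96).
- N = 130: √(130 × 0.36 × 0.64 × 0.90) = 5.19, and 0.45 × 5.19 − 1.96 = 0.38, so power is 64.7%. The slope detectable with 80% power is 2.80/5.19 = 0.54.
- Cox formula, events = 0.36 × 130: 0.45 × √(46.8 × 0.90) − 1.96 = 0.96, so power is 83.2%.
- The plan's worked example ("high WML vs. low WML, $0.45 / 0.36 = 1.25$ or 25% increase") as two proportions, 65 per group: power 17.9%.

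**2. The same effect in 43 placebo participants.**
- Logistic per SD: √(43 × 0.36 × 0.64 × 0.90) = 2.99, and 0.45 × 2.99 − 1.96 = −0.62. Power is 26.9%, so the test misses 73.1% of the time. Assumed placebo nonremission from 0.30 to 0.80 gives 71-80%.
- Simulated logistic fits (standardised tract measure; several runs added the four Section 15.0 covariates and nonremission of 36, 50 and 70%): miss rate 73-78%.
- Cox formula: 0.45 × √(0.36 × 43 × 0.90) − 1.96 = −0.28. Power 39.0%, miss 61%.
- 45% versus 36%, 21.5 per group: power 8.6%, miss 91%.

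**3. Precision of the placebo slope.** The closed-form 95% half-width is 1.96/2.99 = 0.66. Simulation with covariates at zero slope gives about 0.7-0.8. An estimate of exactly zero would therefore still leave 0.45 inside the interval. The slope detectable with 80% power is 2.80/2.99 = 0.94 per SD (odds ratio about 2.6).

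**4. What the interaction gives** (one tract measure, 87 versus 43).
- Slopes 0.45 and 0: SE = √[1/(87 × 0.2304 × 0.90) + 1/(43 × 0.2304 × 0.90)] = √(0.0554 + 0.1122) = 0.409. Then 0.45/0.409 − 1.96 = −0.86, so power is about 19%; simulation and formula together give about 18-22%.
- Equal slopes in both arms: a significant interaction in the predicted direction, together with significance on escitalopram and non-significance on placebo, occurs in about 2-3% of simulated trials. This fits the 2.5% expected in one tail of a 5% test.

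**5. Effect of fitting within-arm models after a significant interaction.** Take assumed true slopes of 1.2 on escitalopram and 0.45 on placebo (1.2 is not in the documents). The interaction is significant in the predicted direction in roughly 32-37% of simulated trials. Within those trials the placebo slope is non-significant 96-98% of the time, against 73-78% without that selection. Conditioning on the interaction favours samples in which the placebo slope came out small.

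**The case against.** The strongest reply is that Section 2.0 states a prediction, not a decision rule. Nothing in Section 15.0 says that a non-significant placebo p-value counts as confirmation. The operative analysis is the interaction, Section 12.0 describes the hypothesis as a difference between arms, and Aim 2 asks whether relationships vary by mechanism of action. That stands: the main comparison is already the right one.

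A reader might infer something stronger: that if tract damage were equally harmful in both arms, the small placebo arm would often produce significance on drug and non-significance on placebo, and the study would report this as drug-specific. The documents do not support that reading. Individual models follow a significant interaction, which holds false drug-specific confirmation under equal slopes to about 2-3% per measure. The small arm also weakens the interaction itself, so small size mostly blocks a drug-specific claim. In the 1.2 versus 0.45 case the slopes truly differ; a drug-specific conclusion would be correct, and only the added statement that tract damage is irrelevant to placebo would be wrong.

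It is also fair that 2:1 allocation, and hence low placebo precision, is a disclosed choice, and that 0.45 per SD is one reading of a figure the plan calls a log hazard ratio.

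What remains is that Hypothesis 3 makes a separate no-effect claim. Section 15.0 never restates it in terms of the interaction, and no planned analysis can establish it.

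**Conclusion.** The point holds as one of wording and reporting. The placebo clause is a no-effect claim with non-significance as its only criterion, in an arm of about 43. The placebo test misses the plan's 0.45 about 73-78% of the time on the per-SD log-odds reading, and 61-91% across the other readings. It is underpowered under every reading tried, so the firm conclusion is low power; the exact percentage depends on the scale of 0.45, two-sided α = 0.05 and the assumed placebo nonremission rate. With a half-width of about 0.7-0.8, a non-significant slope cannot be taken as no relation. The interaction is the right test of difference but cannot show absence, and at about 18-22% power for 0.45 versus 0 it will usually be non-significant too. The finding does not show that the plan is prone to false drug-specific claims.

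**What to change.** 1. In Section 2.0, restate the placebo clause as a contrast: the association of tract WML and FC with nonremission is stronger on escitalopram than on placebo. In Section 15.0, say that it is judged by the drug-by-tract interaction estimate and its 95% CI.
2. Report the placebo-arm slope with its 95% CI whatever the interaction p-value.
3. Pre-state a slope, with its scale, that the placebo CI must exclude before concluding that tract damage does not predict placebo response. Otherwise report that question as inconclusive.

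The cost is wording in two sections and one extra interval per tract measure, with no change to sample size, data collection or treatment. The downside is that the no-placebo-effect claim will usually be inconclusive. At a half-width of 0.7-0.8, a margin of 0.45 could not be met even by an estimate of zero; a zero estimate would exclude only slopes beyond about 0.7-0.8 per SD (odds ratios of about 2.0-2.2, from e^0.7 and e^0.8). The margin should be chosen with that limit acknowledged.
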